### 6.2.4 Concomitant Medications

Throughout the clinical trial, the Investigator may prescribe any concomitant medications or treatments deemed necessary to provide adequate supportive care except for those listed in the exclusion criteria. If they are required, the patient will have to be withdrawn from the study.

**JTA-KOAI - Clinical Study Protocol**

JTA-KOAI-CSP	V 04	Author: EB	Date: May 10, 2017	Pg. 55/114
--------------	------	------------	--------------------	------------

Any medication will be recorded in the eCRF.

### 6.3 Study Follow-up

Safety and efficacy endpoints will be determined in all patients at each scheduled visit over the whole follow-up period.

### 6.4 Packaging and Labelling

Label text will be prepared to meet the requirements of the European Directive (2003/94/EC) and the local regulation, and to maintain the double-blind. All products will be labelled “For Investigational Use Only.”

Regarding the packaging and labelling of investigational medicinal product, a study procedure manual (SPM) for the Principal Investigator including step-by-step instructions and detailed descriptions will be provided to each Investigator before the beginning of the clinical trial. Complete information and training of the participating healthcare professionals will also be conducted during the Site Initiation Visit.

Please refer to the SPM for the Principal Investigator for more details.

### 6.5 Storage

JTA-004 products are manufactured by Bone Therapeutics S.A., Gosselies, Belgium. [REDACTED]

[REDACTED]

[REDACTED] Opened or damaged packages or vials should not be used.

Synvisc-One®, manufactured by Genzyme Corporation, New Jersey, USA are provided in a syringe (no-needle co-packed with it) and should be stored below 30 °C and protected from sunlight and freezing. Opened or damaged packages or syringes should not be used.

### 6.6 Summary of Investigational medicinal products and Reference

A description of investigational medicinal products and reference is summarised in Table 3 below:

## JTA-KOA1 - Clinical Study Protocol

JTA-KOA1-CSP	V 04	Author: EB	Date: May 10, 2017	Pg. 56/114
--------------	------	------------	--------------------	------------

**Table 3: Identity of JTA-004 Investigational medicinal products and Reference**

	JTA-004	Reference
Active substances	Sodium hyaluronate [REDACTED] N-(2,6-dichlorophenyl)-4,5-dihydro-1H-imidazol-2-amine Human plasma	Sodium hyaluronate 48 mg
Volume	2 or 4 ml	6 ml
Strength	50 or 100	NA
Container	Vial	Ready-to-use syringe
Lot number(s)	Provided on the label	Provided on the label
Expiry date	Provided on the label	Provided on the label
Treatment Number	Provided on the label	Provided on the label
Manufacturer	Bone Therapeutics S.A.	Genzyme Corporation
Trade name	NA	Synvisc-One®
Storage requirements	[REDACTED]	below 30 °C

### 6.7 Tracking, Traceability and Accountability of Investigational medicinal products and reference

A tracking system allowing complete traceability of the (JTA-004 and reference) products at all stages will be established and maintained by the Sponsor, Investigator and Monitor.

The Sponsor will keep records to document the physical location of all products from shipment of products to the Investigation Sites until return or disposal.

The Principal Investigator (or authorized designee) must keep accountability records which shall include:

- the date of receipt
- identification of each investigational medicinal product or reference (lot number/serial number)
- the date of use
- patient identification
- the date of return of unused, expired or malfunctioning investigational medicinal products or reference

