**DEFINITIONS OF TERMS**

- **Case Report Form (eCRF):** a printed, optical or electronic document designed to record all of the protocol-required information to be reported to the Sponsor on each trial subject
- **Completed Patient:** a patient who completed all scheduled visits up to last scheduled visit (inclusive)
- **Contract Research Organisation (Monitor):** a person or an organisation contracted by the Sponsor to perform one or more of the Sponsor's trial-related duties and functions
- **Coordinating Investigator:** Investigator who is appointed by the Sponsor to coordinate work in a multicentre clinical study
- **Discontinued or withdrawn patient:** a patient who has been enrolled, screened, randomised, or treated but has withdrawn from the study before completion of the last scheduled visit
- **Double-blinding:** double-blinding is a procedure in which the patient, the Investigator, the monitor, and data analyst are kept unaware of the treatment assignments
- **Data Safety Monitoring Board (DSMB):** An independent data monitoring committee established by the Sponsor to assess at intervals the progress of a clinical trial, the safety data, and the critical efficacy endpoints, and to recommend to the Sponsor whether to continue, modify or stop the trial
- **Endpoint(s):** indicator(s) used for assessing the primary hypothesis of a study
- **Eligible patient:** screened patient (having signed and dated the informed consent form) who is considered eligible according to selection criteria
- **Enrolled patient:** patient who has dated and signed the Informed Consent Form
- **Ethics Committee (EC):** A review panel that is responsible for ensuring the protection of the rights, safety, and well-being of human subjects involved in a clinical trial and is adequately constituted to provide assurance of that protection
- **Good Clinical Practice (GCP):** set of internationally recognized ethical and scientific requirements and standards as regards to the design, conduct, performance, monitoring, auditing, recording, analyses, and reporting of clinical trials, that provides assurance that

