**JTA- KOA1 - Clinical Study Protocol**

JTA-KOA1-CSP	V 04	Author: EB	Date: May 10, 2017	Pg. 36/114
--------------	------	------------	--------------------	------------

(IWRS). The IWRS will only be accessible through a secure website to authorised users with valid login and password.

Once the eligibility and participation of the patient has been confirmed:

- The IWRS will determine the treatment group of the patient and allocate a treatment number to the patient in order to associate a specific treatment (IMP or Reference) to a specific patient.
- A notification of the treatment number without reference to the nature of the treatment (blinded notification) will be sent to the Principal Investigator and Sponsor's representative.
- A notification of the treatment number with the nature of the treatment (unblinded notification) will be sent to the Sponsor's Production Manager in order to label the treatment with the treatment number but also to the local Pharmacist and the Independent Physician.

*Treatment Preparation, Patient Treatment and Blinding of the Study*

Not later than the day before the treatment Visit #2, the kit containing the treatment (IMP or reference product) labelled with the treatment number will be shipped to the Hospital Pharmacy. The IMP will be reconstituted by the pharmacist of the hospital at the request of the Independent Physician. The reference product does not need reconstitution but the Independent Physician must also require the preparation by the local. Before the injection time, the Study Nurse will pick up the reconstituted IMP or the reference product at the Hospital Pharmacy and bring it, into a blinding transfer box, to the Independent Physician.

Although shipping packages will be identical, JTA-004 and reference products will not be provided in the same primary packaging.

The study will be conducted double-blind with reference to the evaluation of trial results.

- The Investigators will be blind to treatment assignments with respect to the patient evaluation. They will recruit, include and assess patients during the whole study follow-up period, but will not treat the patients. Investigators will therefore not be aware of treatment assignment.

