**JTA- KOA1 - Clinical Study Protocol**

JTA-KOA1-CSP	V 04	Author: EB	Date: May 10, 2017	Pg. 37/114
--------------	------	------------	--------------------	------------

- Patients will be blind to treatment assignment, as the four patient groups will undergo the same intra-articular injection (performed by the Independent Physician). As the appearance of the resuspended JTA-004 is different from the reference, appropriate measures must be taken to ensure that the patient is unable to see the injected treatment during the injection procedure. The injection procedure will be identical in all patients.
- Only the Independent Physician and the local Pharmacist will not be blind to treatment assignments, as they will perform the reconstitution or the intra-articular administration of the IMP.

Unblinding is restricted to emergency situations and should only be used under circumstances in which knowledge of the treatment given during the trial is necessary for the proper treatment and medical care of the patient. In the case of medical emergency, decoding will be done for a patient by choosing the “Unblinding” option of the IWRS that allows the user to learn the nature of the treatment taken by a patient in. Under normal circumstances, this option is only available to Principal Investigators/Co-Investigators. In addition, the date of unblinding must be recorded in the appropriate place in the eCRF and signed by the Principal Investigator.

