**JTA-KOA1 - Clinical Study Protocol**

JTA-KOA1-CSP

V 04

Author: EB

Date: May 10, 2017

Pg. 57/114

This tracking system would ensure that investigational medicinal products and reference are tracked and traced during from the order to patient administration, each step being systematically collected, verified, and recorded using specific Forms and Receipts.

The pharmacist of the hospital must ensure that the investigational medicinal products and reference are kept under secure conditions, with access limited to those authorised by the Investigator.

Products accidentally damaged during shipment or at an Investigation Site should be accounted for and documented. It should be noted that all empty vials of JTA-004 and syringes of reference will be kept and stored at each Investigation Site until Monitor verification visits and returned to the Sponsor for destruction once the accountability is performed. Disposal of hazardous material, i.e., syringes and needles, must be conform to applicable laws and regulations. The products must not be used outside the trial.

When the study is completed, all unused products at each Investigation Site will be returned to the Sponsor for destruction.

Finally, data and records required for full traceability will be kept by the Sponsor and Investigator for a minimum of 20 years after clinical use.

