**JTA-KOA1 - Clinical Study Protocol**

JTA-KOA1-CSP

V 04

Author: EB

Date: May 10, 2017

Pg. 89/114

For instance, the following aspects will be closely verified:

- Procurement of signed and dated ICF
- Patient rights, including protection of privacy and confidentiality of personal data and medical records, wellbeing, and safety
- Patient recruitment, eligibility, selection, and inclusion
- Study procedures, including laboratory tests, investigation-related procedures and imaging procedures, if any
- Investigational medicinal product receipt, verification, and final delivery by the Pharmacist
- Investigational medicinal product receipt and verification by the Investigator
- Investigational medicinal product accountability and traceability
- SAE notification and reporting
- Emergency and pregnancy procedures
- Data generation and collection processes
- Accuracy of data collected and recorded in the eCRF
- Facilities and Site staff
- ISF (and other on-site source documentation)

Any detected non-compliance with the protocol, GCP or any other applicable Community and national legal and regulatory requirements will be fully documented by the Monitor with the explanation provided by the Investigator on a deviation log and a Note to File, when applicable. This log will include the patient identification number, the date of deviation occurred and a summary of the deviation. All protocol deviations that have occurred during the study should be classified as minor or major. A patient with a major deviation is not included in the PP.

During the monitoring visits, the Investigator and clinical study staff should be available for questions, verification of data from the source documentation, and possible corrections to the eCRF.

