### **11.3 Source Documents/Data Verification**

To ensure that data in the eCRF are accurate and complete, and in accordance with patient source documents and other source data (e.g., laboratory results reports), 100% of source data verification (SDV) will be performed by the Monitor on all data and eCRF including but not limited to SAE Forms and pregnancy-related documents, consisting in a comparison of the source documentation data with the eCRF and other records relevant to the study. This will require direct access to all original records for each patient.

For the patient questionnaires, 100% SDV will be performed by the Monitor on site. Following this SDV, any errors (discrepancies) greater than 3mm noticed on a VAS during independent verification by/on behalf of the Sponsor (e.g., audits) must trigger appropriate corrective actions to ensure exactness of all VAS values in the study.

The process of obtaining informed consent and the presence on file of the signed and dated ICF will be verified for all patients screened, whether or not they were eligible.

JTA-KOA1 - Clinical Study Protocol				
JTA-KOA1-CSP	V 04	Author: EB	Date: May 10, 2017	Pg. 91/114

The back-transcription of data from the eCRF into source documents is not allowed, including when discrepancies/omissions are detected by SDV.

As some data will be directly entered into the eCRF, the eCRF will be considered as source document for these data. The “Location of Source Data” list will be completed confirming the location of the source data.

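### Product accountability and monitoring procedures contradict the stated blinding of the Monitor, and leave the Investigator's blinding unprotected

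*Combined protocol and SAP*

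**What the plan says.** **Who is blind.** The Definitions of Terms state that "double-blinding is a procedure in which the patient, the Investigator, the monitor, and data analyst are kept unaware of the treatment assignments". Section 3.3.2 says of those who recruit and assess patients: "Investigators will therefore not be aware of treatment assignment". It then closes the list of exceptions: "Only the Independent Physician and the local Pharmacist will not be blind to treatment assignments". Earlier in the same section, however, the notification that reveals the product also goes to the sponsor's Production Manager.

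**Who handles product information.** Section 6.7 says: "The Principal Investigator (or authorized designee) must keep accountability records which shall include" dates of receipt, use and return, the lot or serial number, and patient identification. It gives upkeep of the tracking system jointly to the Sponsor, the Investigator and the Monitor. It adds that "all empty vials of JTA-004 and syringes of reference will be kept and stored at each Investigation Site until Monitor verification visits". Among the items to be closely verified, section 11.2 lists "Investigational medicinal product receipt and verification by the Investigator", separately from receipt and delivery by the Pharmacist, and also lists product accountability and traceability.

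**What else the Monitor does.** Section 11.3 states: "For the patient questionnaires, 100% SDV will be performed by the Monitor on site".

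**The concern.** The protocol takes trouble over blinding elsewhere: identical shipping packages, a blinding transfer box, a separate physician to inject, and concealment of the syringe from the patient. The accountability and monitoring text then gives product-level tasks to two roles that are supposed to be blind.

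The Investigator assesses patients throughout follow-up, judges whether adverse events were caused by the product (8.1.4), prescribes concomitant treatment (6.2.4) and has discretion over withdrawal (9.1). Knowing the arm could colour each of these. The Monitor classifies and documents deviations and verifies the data. If either role learns the allocation, the trial loses part of the double-blind property claimed in its title, and a lost blind cannot be restored afterwards.

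**Working it through.** No figure in the plan bears on this point, so there is nothing to recompute. The check sets the passages side by side.

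1. **Are the Monitor and Investigator meant to be blind?** Yes. The Definitions name both. Section 3.3.2 repeats it for Investigators, and neither role is on its list of unblinded people.

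2. **Does a stated procedure put the product before the Monitor?** Yes. Section 6.7 keeps the used containers for the Monitor's verification visit, and section 11.2 has the Monitor verify accountability.

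3. **Does a used container show the arm?** It separates JTA-004 from the reference. Section 3.3.2 says the primary packaging differs. Table 3 gives a vial of 2 or 4 ml against a ready-to-use syringe of 6 ml, from different manufacturers. Section 6.4 says label text will preserve the blind, but a label cannot hide the type of container.

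4. **Can the container be tied to a patient?** Table 3 puts the treatment number on the label of both products, and section 3.3.2 has the IWRS link that number to one patient. Section 6.7 puts patient identification in the accountability record. Reconciling containers against records therefore gives a patient-level allocation to JTA-004 or reference, provided the number stays with the used container or the record makes the link.

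5. **Does a stated procedure put the product before the Investigator?** Less directly.
   - The records in 6.7 may be kept by the Principal Investigator or by a designee. The text permits the Pharmacist but does not require it.
   - The listed fields do not include container, volume or manufacturer. A lot or serial number reveals the arm only to someone who can link it to a product.
   - The 11.2 item names the Investigator and sits beside a separate Pharmacist item, so it cannot be read as meaning the Pharmacist. It conflicts with 3.3.2, where product goes from the pharmacy to the Independent Physician without passing through the Investigator.
   - Used containers are stored at the site. No text shows them to the Investigator.

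6. **Is there a safeguard?** The readable text has no unblinded monitor, no restriction of records to the pharmacy, and no separation of container checks from data verification.

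7. **Reach.** Accountability is per patient, so the exposure could cover every treated patient: up to 4 × 41 = 164 as planned in section 10.9.

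**The case against.** The strongest case against is that a site can comply with section 6.7 without unblinding the Investigator. It names the Pharmacist as designee; the Pharmacist already has secure custody of the products under 6.7 and reconstitutes JTA-004. The 11.2 item is one example in a monitoring list, not an instruction to investigators, and may be carried-over text: the same section refers to human tissues and cells. The Definitions allow the Monitor to be an organisation, so container checks and questionnaire verification need not fall to one individual. Safeguards may also lie in redacted text or in the study procedure manual to which section 6.4 refers.

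Most of this stands, and it limits the point for the Investigator. It does not remove the conflict over the Monitor, because the Definitions make that role blind without distinguishing individuals. Nor does it turn a permitted delegation into a required one.

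A reader might infer three stronger things that the documents do not support:

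- **That any site following 6.7 necessarily unblinds the Principal Investigator.** The designee wording and the uncertain link from lot number to product rule this out.
- **That the primary endpoint is directly exposed through the Monitor's check of the VAS readings.** Patients are kept from seeing the injection (3.3.2), complete the questionnaires alone and before any discussion (3.4.1), and the original pages are kept as source (11.1). A Monitor can re-measure a mark but not move it.
- **That the 3 mm discrepancy limit in 11.3, set against the planned 7 mm difference, measures the possible bias (3/7 = 43%).** The 3 mm triggers corrective action on a single reading at independent verification; the 7 mm is a difference between group means. Their ratio says nothing about bias from unblinding.

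**Conclusion.** The plan contradicts itself. As written, the Monitor's blind is broken by a stated procedure. The Investigator's is contradicted by one item in section 11.2 and left unprotected by section 6.7, but it is not shown to be lost.

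The effect on results cannot be put into a number from the documents. Up to 164 patients could be affected, and what a container reveals is JTA-004 against reference, which is the contrast tested in the superiority analysis. The main risk is to causality assessment, concomitant treatment and withdrawal decisions; the self-reported pain score is comparatively well protected.

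The conclusion about the Monitor assumes that used containers are inspected as containers and can be matched to patients. The conclusion about the Investigator assumes that no unseen text restricts the records to unblinded staff. If the study procedure manual already does so, the protocol still has to be brought into line with it.

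The unblinded list in 3.3.2 is also incomplete, since the Production Manager receives the allocation. This is a smaller point of wording, because the notification itself is openly described.

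**What to change.** - **Section 6.7:** require the local Pharmacist, already unblinded, to keep the accountability records and used containers in the pharmacy, closed to Investigators and anyone who assesses patients.
- **Section 11.2:** delete receipt and verification by the Investigator, or limit it to the blinded treatment number. Limit the blinded Monitor to treatment-number checks.
- **Product-level reconciliation:** assign it to the sponsor's Production Manager, already unblinded, during the study and with no discussion of allocation with the study team. Waiting until database lock would protect the blind equally well but would find dispensing errors late, which matters because section 10.1 analyses safety as treated.
- **Section 3.3.2:** add the Production Manager to the list of unblinded people.
- If the study procedure manual already contains such safeguards, refer to them in these sections.

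The cost is protocol wording and a revised accountability log. No new staff are needed, although the Production Manager takes on a task. The downside is that product-level checks move away from the routine monitoring visit.

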**JTA-KOA1 - Clinical Study Protocol**

JTA-KOA1-CSP

V 04

Author: EB

Date: May 10, 2017

Pg. 57/114

This tracking system would ensure that investigational medicinal products and reference are tracked and traced during from the order to patient administration, each step being systematically collected, verified, and recorded using specific Forms and Receipts.

The pharmacist of the hospital must ensure that the investigational medicinal products and reference are kept under secure conditions, with access limited to those authorised by the Investigator.

Products accidentally damaged during shipment or at an Investigation Site should be accounted for and documented. It should be noted that all empty vials of JTA-004 and syringes of reference will be kept and stored at each Investigation Site until Monitor verification visits and returned to the Sponsor for destruction once the accountability is performed. Disposal of hazardous material, i.e., syringes and needles, must be conform to applicable laws and regulations. The products must not be used outside the trial.

When the study is completed, all unused products at each Investigation Site will be returned to the Sponsor for destruction.

Finally, data and records required for full traceability will be kept by the Sponsor and Investigator for a minimum of 20 years after clinical use.

